5.3.2 Timing of Dose Administration

Trial treatment should be administered on Day 1 of each cycle after all procedures/assessments have been completed as detailed on the Trial Flow Chart (Section 6.0). Trial treatment may be administered up to 3 days before or after the scheduled Day 1 of each cycle due to administrative reasons.

All trial treatments will be administered on an outpatient basis.

Pembrolizumab 200 mg will be administered as a 30 minute IV infusion every 3 weeks. Sites should make every effort to target infusion timing to be as close to 30 minutes as possible. However, given the variability of infusion pumps from site to site, a window of -5

minutes and +10 minutes is permitted (i.e., infusion time is 30 minutes: -5 min/+10 min). Pembrolizumab will be administered before Lenalidomide. There is no required waiting time between administration of both drugs.

The package insert contains specific instructions for the preparation of the pembrolizumab infusion fluid and administration of infusion solution.

Lenalidomide will be administered at a starting dose of 15mg PO daily, from day 1 to 14, every 21 days, following a dose escalation protocol as per trial design.

5.3.3 Trial Blinding/Masking

This is an open-label trial; therefore, the Sponsor, investigator and subject will know the treatment administered.

5.4 Concomitant Medications/Vaccinations (allowed & prohibited)

Medications or vaccinations specifically prohibited in the exclusion criteria are not allowed during the ongoing trial. If there is a clinical indication for one of these or other medications or vaccinations specifically prohibited during the trial, discontinuation from trial therapy or vaccination may be required. The investigator should discuss any questions regarding this with the Merck Clinical team. The final decision on any supportive therapy or vaccination rests with the investigator and/or the subject's primary physician.

5.4.1 Acceptable Concomitant Medications

All treatments that the investigator considers necessary for a subject's welfare may be administered at the discretion of the investigator in keeping with the community standards of medical care. All concomitant medication will be recorded on the case report form (CRF) including all prescription, over-the-counter (OTC), herbal supplements, and IV medications and fluids. If changes occur during the trial period, documentation of drug dosage, frequency, route, and date may also be included on the CRF.

All concomitant medications received within 28 days before the first dose of trial treatment and 30 days after the last dose of trial treatment should be recorded. Concomitant medications administered after 30 days after the last dose of trial treatment should be recorded for SAEs and ECIs as defined in Section 7.2.

5.4.2 Prohibited Concomitant Medications

Subjects are prohibited from receiving the following therapies during the Screening and Treatment Phase (including retreatment for post-complete response relapse) of this trial:

- Antineoplastic systemic chemotherapy or biological therapy

- Immunotherapy not specified in this protocol
- Chemotherapy not specified in this protocol
- Investigational agents other than pembrolizumab
- Radiation therapy
 - Note: Radiation therapy to a symptomatic solitary lesion or to the brain may be allowed at the investigator's discretion.
- Live vaccines within 30 days prior to the first dose of trial treatment and while participating in the trial. Examples of live vaccines include, but are not limited to, the following: measles, mumps, rubella, varicella/zoster, yellow fever, rabies, BCG, and typhoid vaccine.
- Systemic glucocorticoids for any purpose other than to modulate symptoms from an event of clinical interest of suspected immunologic etiology. The use of physiologic doses of corticosteroids may be approved after consultation with the Sponsor.

Subjects who, in the assessment by the investigator, require the use of any of the aforementioned treatments for clinical management should be removed from the trial. Subjects may receive other medications that the investigator deems to be medically necessary.

The Exclusion Criteria describes other medications which are prohibited in this trial.

There are no prohibited therapies during the Post-Treatment Follow-up Phase.

5.5 Rescue Medications & Supportive Care

5.5.1 Supportive Care Guidelines

Subjects should receive appropriate supportive care measures as deemed necessary by the treating investigator. Suggested supportive care measures for the management of adverse events with potential immunologic etiology are outlined below and in greater detail in the ECI guidance document. Where appropriate, these guidelines include the use of oral or intravenous treatment with corticosteroids as well as additional anti-inflammatory agents if symptoms do not improve with administration of corticosteroids. Note that several courses of steroid tapering may be necessary as symptoms may worsen when the steroid dose is decreased. For each disorder, attempts should be made to rule out other causes such as metastatic disease or bacterial or viral infection, which might require additional supportive care. The treatment guidelines are intended to be applied when the investigator determines the events to be related to pembrolizumab.

Note: if after the evaluation the event is determined not to be related, the investigator is instructed to follow the ECI reporting guidance but does not need to follow the treatment guidance (as outlined in the ECI guidance document). Refer to Section 5.2.1 for dose modification.

It may be necessary to perform conditional procedures such as bronchoscopy, endoscopy, or skin photography as part of evaluation of the event. Suggested conditional procedures, as appropriate, can be found in the ECI guidance document.

- **Pneumonitis:**

- For **Grade 2 events**, treat with systemic corticosteroids. When symptoms improve to Grade 1 or less, steroid taper should be started and continued over no less than 4 weeks.
- For **Grade 3-4 events**, immediately treat with intravenous steroids. Administer additional anti-inflammatory measures, as needed.
- Add prophylactic antibiotics for opportunistic infections in the case of prolonged steroid administration.

- **Diarrhea/Colitis:**

Subjects should be carefully monitored for signs and symptoms of enterocolitis (such as diarrhea, abdominal pain, blood or mucus in stool, with or without fever) and of bowel perforation (such as peritoneal signs and ileus).

- All subjects who experience diarrhea/colitis should be advised to drink liberal quantities of clear fluids. If sufficient oral fluid intake is not feasible, fluid and electrolytes should be substituted via IV infusion. For Grade 2 or higher diarrhea, consider GI consultation and endoscopy to confirm or rule out colitis.
- For **Grade 2 diarrhea/colitis** that persists greater than 3 days, administer oral corticosteroids.
- For **Grade 3 or 4 diarrhea/colitis** that persists > 1 week, treat with intravenous steroids followed by high dose oral steroids.

- When symptoms improve to Grade 1 or less, steroid taper should be started and continued over no less than 4 weeks.
- **Type 1 diabetes mellitus (if new onset, including diabetic ketoacidosis [DKA]) or \geq Grade 3 Hyperglycemia, if associated with ketosis (ketonuria) or metabolic acidosis (DKA)**
 - For **T1DM** or **Grade 3-4** Hyperglycemia
 - Insulin replacement therapy is recommended for Type I diabetes mellitus and for Grade 3-4 hyperglycemia associated with metabolic acidosis or ketonuria.
 - Evaluate patients with serum glucose and a metabolic panel, urine ketones, glycosylated hemoglobin, and C-peptide.
- **Hypophysitis:**
 - For **Grade 2** events, treat with corticosteroids. When symptoms improve to Grade 1 or less, steroid taper should be started and continued over no less than 4 weeks. Replacement of appropriate hormones may be required as the steroid dose is tapered.
 - For **Grade 3-4** events, treat with an initial dose of IV corticosteroids followed by oral corticosteroids. When symptoms improve to Grade 1 or less, steroid taper should be started and continued over no less than 4 weeks. Replacement of appropriate hormones may be required as the steroid dose is tapered.
- **Hyperthyroidism or Hypothyroidism:**

Thyroid disorders can occur at any time during treatment. Monitor patients for changes in thyroid function (at the start of treatment, periodically during treatment,

and as indicated based on clinical evaluation) and for clinical signs and symptoms of thyroid disorders.

- **Grade 2** hyperthyroidism events (and **Grade 2-4** hypothyroidism):
 - In hyperthyroidism, non-selective beta-blockers (e.g. propranolol) are suggested as initial therapy.
 - In hypothyroidism, thyroid hormone replacement therapy, with levothyroxine or liothyronine, is indicated per standard of care.
- **Grade 3-4** hyperthyroidism
 - Treat with an initial dose of IV corticosteroid followed by oral corticosteroids. When symptoms improve to Grade 1 or less, steroid taper should be started and continued over no less than 4 weeks. Replacement of appropriate hormones may be required as the steroid dose is tapered.
- **Hepatic:**
 - For **Grade 2** events, monitor liver function tests more frequently until returned to baseline values (consider weekly).
 - Treat with IV or oral corticosteroids
 - For **Grade 3-4** events, treat with intravenous corticosteroids for 24 to 48 hours.
 - When symptoms improve to Grade 1 or less, a steroid taper should be started and continued over no less than 4 weeks.
- **Renal Failure or Nephritis:**
 - For **Grade 2** events, treat with corticosteroids.
 - For **Grade 3-4** events, treat with systemic corticosteroids.

- When symptoms improve to Grade 1 or less, steroid taper should be started and continued over no less than 4 weeks.

Management of Infusion Reactions: Signs and symptoms usually develop during or shortly after drug infusion and generally resolve completely within 24 hours of completion of infusion.

Table 5 below shows treatment guidelines for subjects who experience an infusion reaction associated with administration of pembrolizumab (MK-3475).

Table 5 Infusion Reaction Treatment Guidelines

NCI CTCAE Grade	Treatment	Premedication at subsequent dosing

Grade 1
 
Mild reaction; infusion interruption not indicated; intervention not indicated
	
Increase monitoring of vital signs as medically indicated until the subject is deemed medically stable in the opinion of the investigator.
	
None


Grade 2
 
Requires infusion interruption but responds promptly to symptomatic treatment (e.g., antihistamines, NSAIDS, narcotics, IV fluids); prophylactic medications indicated for <=24 hrs
	
Stop Infusion and monitor symptoms.
 
Additional appropriate medical therapy may include but is not limited to:
 
 IV fluids Antihistamines NSAIDS Acetaminophen Narcotics 
Increase monitoring of vital signs as medically indicated until the subject is deemed medically stable in the opinion of the investigator.
 
If symptoms resolve within one hour of stopping drug infusion, the infusion may be restarted at 50% of the original infusion rate (e.g., from 100 mL/hr to 50 mL/hr). Otherwise dosing will be held until symptoms resolve and the subject should be premedicated for the next scheduled dose.
	
Subject may be premedicated 1.5h (± 30 minutes) prior to infusion of pembrolizumab (MK-3475) with:
 
Diphenhydramine 50 mg po (or equivalent dose of antihistamine).
 
Acetaminophen 500-1000 mg po (or equivalent dose of antipyretic).

NCI CTCAE Grade	Treatment	Premedication at subsequent dosing
	
Subjects who develop Grade 2 toxicity despite adequate premedication should be permanently discontinued from further trial treatment administration.
	

Grades 3 or 4
 
Grade 3: Prolonged (i.e., not rapidly responsive to symptomatic medication and/or brief interruption of infusion); recurrence of symptoms following initial improvement; hospitalization indicated for other clinical sequelae (e.g., renal impairment, pulmonary infiltrates)
 
Grade 4: Life-threatening; pressor or ventilatory support indicated
	
Stop Infusion.
 
Additional appropriate medical therapy may include but is not limited to:
 
 IV fluids Antihistamines NSAIDS Acetaminophen Narcotics Oxygen Pressors Corticosteroids Epinephrine 
Increase monitoring of vital signs as medically indicated until the subject is deemed medically stable in the opinion of the investigator.
 
Hospitalization may be indicated.
 
Subject is permanently discontinued from further trial treatment administration.
	
No subsequent dosing

Appropriate resuscitation equipment should be available in the room and a physician readily available during the period of drug administration.
		

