5.3.1.3 Definition of Dose-Limiting Toxicity

Toxicities should be attributable to the study intervention to constitute a dose limiting toxicity (DLT). Toxicity will be graded using the Common Toxicity Criteria for Adverse Events (CTCAE) version 4.0. A DLT is defined by the occurrence of any of the following toxicities (CTCAE v.4.03) for up to 21 days from initiation of the combination therapy (i.e. within the first cycle of therapy) in order to evaluate the potential toxicities of these therapies.

Non-Hematological dose-limiting toxicity

Any Grade 3 or Grade 4 non-hematological toxicity that is possibly, probably or definitely attributable to the regimen pembrolizumab-lenalidomide is considered a DLT, including the following:

- Any type of grade 3-4 hypersensitivity reaction (i.e.: allergic reaction, anaphylaxis, serum sickness, skin disorders, etc.), regardless of attribution.
- Any type of grade 3-4 immune related adverse event
- Inability to receive pembrolizumab-lenalidomide therapy within a 1 month period of scheduled treatment, due to a therapy related event.
- Grade 3 nausea/vomiting/diarrhea lasting longer than 24hours despite maximal care or Grade 4 nausea/vomiting/diarrhea

Any other non-hematologic clinical toxicity considered at least possibly related to treatment defined as any Grade 3 or greater with the specific exception of:

- Grade 3 dehydration that, in the opinion of the investigator, occurs in the setting of inadequate prophylactic measures or compliance with supportive care measures and lasts for less than 48 hours
- Grade 3 fatigue or Grade 4 fatigue that lasts for ≤ 5 days
- Grade 3 fever
- Grade 3 ALT/AST elevation for which total bilirubin remains within normal limits.

Hematologic dose-limiting toxicity

The following hematological toxicity possibly, probably or definitely attributable to the regimen of pembrolizumab and lenalidomide is considered a DLT. Growth factors are allowed per treating investigator's discretion in patients at high risk for febrile neutropenia.

- Grade 4 neutropenia associated with fever (> 38.5) of any duration
- Grade 3 neutropenia associated with fever (> 38.5) of any duration
- Grade 4 thrombocytopenia or Grade 3 thrombocytopenia with bleeding or any requirement for platelet transfusion.
- Grade 4 anemia unexplained by underlying disease
- Myelosuppression that causes a delay of > 7 days in next cycle of pembrolizumab/lenalidomide

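### Section 5.5.1 sets a later suggested steroid trigger for Grade 3-4 diarrhea/colitis (more than 1 week) than for Grade 2 (more than 3 days)

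*Combined protocol and SAP*

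**What the plan says.** The diarrhea/colitis block of section 5.5.1 (Supportive Care Guidelines) has two bullets that say when to start steroids.

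- Grade 2 diarrhea/colitis "that persists greater than 3 days, administer oral corticosteroids".
- Grade 3 or 4 diarrhea/colitis "that persists > 1 week, treat with intravenous steroids followed by high dose oral steroids".

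The opening of the section fixes when this advice applies: "The treatment guidelines are intended to be applied when the investigator determines the events to be related to pembrolizumab". It also describes the measures as suggested, leaves care to the treating investigator, and refers to the ECI guidance document for more detail. Sections 6.2.2.1 and 6.3.1.2 place that document in Appendix 4.

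**The concern.** A persistence condition on steroid treatment should not lengthen as the event becomes more severe. Table 7 describes Grade 3 as severe, with hospitalization indicated, and Grade 4 as life-threatening, with urgent intervention indicated. A condition of more than one week fits neither description. The diarrhea/colitis block itself asks sites to watch for bowel perforation.

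The stake is patient safety. A site that followed this bullet alone would start steroids later in a Grade 3-4 event than in a Grade 2 event. Read literally, a patient who worsens from Grade 2 to Grade 3 within the first three days moves from the 3-day trigger to the 1-week trigger. Nothing here bears on the dose-escalation rules, the complete response endpoint, the sample size or the error rates.

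**Working it through.** The plan gives no figure of its own to reproduce. The check is a comparison of texts and one subtraction.

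**Step 1. Inputs, both from section 5.5.1, diarrhea/colitis.**
- Grade 2 threshold: more than 3 days, oral steroids.
- Grade 3-4 threshold: more than 1 week, which is 7 days, IV then high-dose oral steroids.

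**Step 2. Gap.** Grade 3-4 threshold minus Grade 2 threshold = 7 - 3 = 4 days later for the more severe grades.

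**Step 3. Does another bullet in the block give an earlier start?** No. The rest covers monitoring, fluids, GI consultation and endoscopy (to be considered from Grade 2 upward), and the steroid taper.

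**Step 4. The other immune events in section 5.5.1 with steroids advised at Grade 3-4.**

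| Event | Advice at Grade 3-4 | Waiting period |
|---|---|---|
| Pneumonitis | "immediately treat with intravenous steroids" | none |
| Hypophysitis | IV, then oral steroids | none |
| Hyperthyroidism | IV, then oral steroids | none |
| Hepatic | IV steroids for 24 to 48 hours (length of treatment, not a wait) | none |
| Renal failure or nephritis | systemic steroids | none |
| Diarrhea/colitis | IV, then high-dose oral steroids | more than 1 week |

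Diarrhea/colitis is the only exception among the six.

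**Step 5. Could a pause for diagnosis explain the longer wait?** Section 5.5.1 asks sites to try to rule out other causes, including infection. That instruction covers every disorder in the section, so it applies equally to Grade 2 diarrhea, where the threshold is 3 days. It also applies to the five other events above, which have no wait at Grade 3-4. The treatment advice is meant for events already judged related to pembrolizumab. A diagnostic pause therefore gives no reason for a longer wait at the higher grades.

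**Step 6. What is not delayed.** Fluids and the consideration of GI work-up have no waiting period. Table 3 holds pembrolizumab for Grade 2-3 diarrhea/colitis and stops it permanently for Grade 4, again without a wait. The inversion concerns steroid timing alone.

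**The case against.** The strongest case against the point is that this is advice and that nothing stops a site from acting sooner. The bullet says what to do once the event has lasted more than a week; it does not forbid steroids before then. Section 5.4.2 prohibits "Systemic glucocorticoids for any purpose other than to modulate symptoms from an event of clinical interest of suspected immunologic etiology", so steroids for a suspected immune event are allowed, with no minimum duration. Section 5.4 adds that "The final decision on any supportive therapy or vaccination rests with the investigator" and/or the primary physician. A clinician facing Grade 4 diarrhea is unlikely to wait a week because of one bullet. The ECI guidance document may also already give sites a correct and more detailed rule.

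Much of this stands. A reader might infer that the protocol makes Grade 3-4 patients wait a week. The documents do not support that, because earlier treatment is permitted. It also cannot be said that sites lack a correct rule, because the text of Appendix 4 is not in the copy reviewed.

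What does not stand is that these points make the bullet acceptable. Permission to depart from advice does not justify advice that points the wrong way. If the ECI document advises earlier steroids, sites hold two inconsistent instructions. If it repeats this bullet, the inversion is in both places. Either way this bullet needs correcting.

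**Conclusion.** The point holds for the wording of this bullet. The suggested steroid threshold is 4 days later for Grade 3-4 than for Grade 2, and it departs from the no-wait pattern used for the five other Grade 3-4 events. The conclusion assumes only that one week means 7 days and that the two bullets are read as written. It should be fixed: it is a stated rule on patient safety that runs in the wrong direction. Confidence is high on the text and low on the practical consequence.

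Three stronger readings are tempting but not supported.

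- **A longer delay measured against the dose-limiting toxicity rule.** Section 5.3.1.3 counts "Grade 3 nausea/vomiting/diarrhea lasting longer than 24hours despite maximal care or Grade 4 nausea/vomiting/diarrhea" and also "Any type of grade 3-4 immune related adverse event". A reader might subtract 24 hours, or onset, from the 7 days. That rule classifies cycle 1 events for dose escalation. It does not say when steroids start, or that maximal care includes them. The difference is not a treatment delay.
- **A conflict with Table 3.** Stopping pembrolizumab for Grade 4 and starting steroids are separate, compatible actions.
- **A count of affected patients.** The background section gives immune-related diarrhea in 2.2% under single-agent pembrolizumab. Applied to 26-29 patients this is 0.022 x 26 = 0.6 to 0.022 x 29 = 0.6 cases. The figure is not split by grade and does not come from this combination or from lymphoma, so it does not estimate how many patients would be treated late.

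**What to change.** Delete the one-week persistence condition from the Grade 3-4 bullet. Suggested sense of the replacement: *Grade 3 or 4 diarrhea/colitis judged related to pembrolizumab is treated promptly with IV steroids and then high-dose oral steroids, in any case no later than the Grade 2 trigger.*

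The reference to the Grade 2 trigger is an outer limit, not a target. Prompt treatment without a set wait is what matches the other Grade 3-4 events in the section. The clinical team should settle the exact wording and align it with the ECI guidance document, so that sites see one rule.

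The cost is one edited bullet, a check against one existing document, and a clarification letter to sites until the next amendment. No design or analysis element changes.

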5.6 Diet/Activity/Other Considerations

5.6.1 Diet

Subjects should maintain a normal diet unless modifications are required to manage an AE such as diarrhea, nausea or vomiting.

5.6.2 Contraception

Lenalidomide may cause severe birth defects or death of the fetus if used during pregnancy. Lenalidomide is similar to thalidomide, which causes life-threatening birth defects. Pembrolizumab may have adverse effects on a fetus in utero, too. Furthermore, it is not known if pembrolizumab has transient adverse effects on the composition of sperm. Non-pregnant, non-breast-feeding women may be enrolled if they are willing to use 2 methods of birth control or are considered highly unlikely to conceive. Highly unlikely to conceive is defined as 1) surgically sterilized, or 2) postmenopausal (a woman who is ≥ 45 years of age and has not had menses for greater than 1 year will be considered postmenopausal), or 3) not heterosexually active for the duration of the study. The two birth control methods can be either two barrier methods or a barrier method plus a hormonal method to prevent pregnancy. Subjects should start using birth control from study Visit 1 throughout the study period up to 120 days after the last dose of study therapy.

The following are considered adequate barrier methods of contraception: diaphragm, condom (by the partner), copper intrauterine device, sponge, or spermicide. Appropriate hormonal contraceptives will include any registered and marketed contraceptive agent that contains an estrogen and/or a progestational agent (including oral, subcutaneous, intrauterine, or intramuscular agents).

Subjects should be informed that taking the study medication may involve unknown risks to the fetus (unborn baby) if pregnancy were to occur during the study. In order to participate in the study they must adhere to the contraception requirement (described above) for the duration of the study and during the follow-up period defined in section 7.2.2-Reporting of Pregnancy and Lactation to the Sponsor and to Merck. If there is any question that a subject will not reliably comply with the requirements for contraception, that subject should not be entered into the study.

